Our laboratory has vast experience in working with human adipose tissue/cell metabolism, inflammation, morphology, and differentiation. We have established a working relationship with the cardiac surgery team and recently completed a study in 24 subjects with myocardial bridge, in whom we sampled five fat depots, including three from the epicardium, over vessels with and without atherosclerotic plaque. Gene expression (60 genes via Nanostring) and cytokine secretion analyses are in process. We also have spent over a decade performing collagenase digestion of subcutaneous and visceral human fat to isolate mature adipocytes for measurement of insulin-mediated glucose uptake (IMGU) and lipolysis, and stromal-vascular cells for flow cytometry and preadipocyte differentiation (methods published). We thus have the infrastructure, interdisciplinary relationships, wet lab space and methods, and scientific expertise in adipocyte biology and metabolism to investigate the effects of ertugliflozin on epicardial fat. We hypothesize that ertugliflozin will enhance lipolysis, improve insulin sensitivity, decrease adipose cell size, and reverse inflammatory phenotype in EAT.

References

3. [name], Carter S, Lamendola C, et al. Effects of moderate variations in macronutrient composition on weight loss and reduction in cardiovascular disease risk in obese, insulin-resistant adults. *Am J Clin Nutr* 2006; 84:813-21.
4. [name] et al. Effect of Low Carbohydrate Weight Loss Diet on Adipose Cell Size. 1709P. American Diabetes Association 2016, New Orleans, LA.
5. Iacobellis G. Local and systemic effects of the multifaceted epicardial adipose tissue depot. *Nat Rev Endocrinol*. 2015; 11:363-71.

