We hypothesize that SGLT2i treatment reduces cardiovascular risk via changes in epicardial adipose tissue (EAT) that yield smaller adipocytes with increased insulin sensitivity, capacity for lipid metabolism (metabolic flexibility) including FFA release via isoproterenol-stimulated lipolysis, which provides fuel for the myocardium during times of increased need, and decreased inflammation, which reduces atherosclerotic plaque and plaque instability.

Study Design/Clinical Plan

- Provide a concise overview stating the type of experimental design

[figure not shown]
1. Test indirect effects of ertugliflozin on EAT: Because ertugliflozin lowers glucose renally, and thus does not invoke insulin secretion, ambient insulin concentrations are lower and FFA higher than other glucose-lowering therapies such as sulfonylureas. Insulin represents a metabolic switch from fasting (low insulin, catabolic, energy releasing) metabolism to fed (high insulin, anabolic, energy storing) metabolism, and the cardiovascular benefits of SGLT2i may be related to a switch in systemic metabolism from high to low insulin state, thereby promoting FFA release from EAT, thereby increasing energy substrate for myocardium, shrinking epicardial adipocytes, enhancing glucose uptake and insulin sensitivity, and decreasing inflammation. Because these patients were unable to take

the drug due to insufficient lead time prior to surgery, we decided to use these patients to test direct effects of ertugliflozin on EAT.

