2. Test direct effects of ertugliflozin on EAT: Harvest fat from epicardial, pericardial, and subcutaneous (chest wall) depots from patients (with or without CAD and with or without type 2 diabetes) undergoing cardiothoracic surgery. Explants of whole tissue and/or collagenase digested mature fat cells will be used to measure lipolysis (basal/isoproterenol-stimulated/insulin-suppressed conditions), secretome (basal conditions only), and gene expression under mock vs drug-treated culture conditions for 2-24 hours¹⁷. In addition, mature adipocytes freshly isolated from collagenase digestion will be obtained from bariatric surgery patients from both SAT and VAT. This is necessary because bariatric samples yield greater quantities of fat for collagenase digestion whereas epicardial fat sample quantities are smaller which necessitates conducting an explant experiment on the tissue. Mature cells from bariatric samples will be tested for lipolysis, insulin-mediated glucose uptake, gene expression, and inflammatory cytokine secretion under mock vs drug-treated culture conditions for 2-24 hours. VAT has many similar qualities to EAT since they are both visceral depots, and thus will augment any results obtained from EAT and provide a mechanism for isolated mature fat cells which otherwise is not possible. In the case of minimal EAT availability from surgical collection, an explant culture will be performed to differentiate stromal vascular cells into the necessary amount of mature fat cells for a lipolysis assay. This experiment addresses the direct effect of ertugliflozin on EAT in the absence of systemic changes such as lower glucose, insulin, and higher FFA concentrations. Due to small amounts of EAT, we will also conduct lipolysis assays on whole tissue explants from all three depots.

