SVCs are pelleted by centrifugation, erythrocytes lysed, and the isolated cells are seeded onto 12-well plates at a density of 10,000 cells per well for assessment of adipogenesis. Adipogenic differentiation medium purchased from Zenbio (Cat#DM2 for subcutaneous depot cells and #OMDM for visceral depot cells) are used to induce differentiation. ERTUGLIFLOZIN and vehicle are supplemented to the adipogenic differentiation medium. At 3 days, medium is changed to maintenance medium from ZenBio (Cat#AM-1) based on the manufacturer's protocol and ertugliflozin is supplemented. Differentiation is carried out for 14 days to achieve terminal differentiation as described^{17,18}.

6) Optimization of ertugliflozin concentration for pre-adipocyte culture studies

SVC are placed in wells with vehicle control and three different concentrations of ERTUGLIFLOZIN (provided by the company). Planned concentrations to test include 10, 100 and 300nmol/L. Media (with or with drug at the listed concentrations)

will be changed every other day with media replenishment. BrdU can be used to determine the proliferation effect at day 3 and day 7. Optimal concentration will be defined as the concentration that yields 50% of growth inhibition.

7) IMGU using 2NDGB method for cultured adipocytes

Assay of Insulin Mediated Glucose Uptake (IMGU) is carried out after 14 days of adipogenic differentiation. On day 14 terminally-differentiated cells are washed with glucose-free PBS three times to remove the residual glucose in the media. Glucose-free PBS is used to fast the cells for additional one hour at 37C. After one hour incubation, 10ug/ml of insulin is added to the cells to stimulate the glucose release, after 10 mins, 100ug/ml of 2-NDBG solution is added to the cells for fluorescence labeling. 30 mins later, cells are washed with PBS twice to remove the residual 2NDBG in the buffer and cells are lysed in the protein lysis buffer (Sigma, Inc). Subsequently, 100ul of lysis are read by excitation/emission=485/535nm to detect the fluorescence incorporation to the cells. The protein lysis concentration are measured by Coomassie Plus™ Protein Assay. Each samples fluorescence reading is normalized by its protein concentration as the final reading. Each assay is set to have three replicates, mean and SD are calculated compared to the control.

8) Total fat uptake using Oil Red O on day 14 of culture

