IMGU assay of mature adipocyte is carried by using the isolated PCV of mature cells after digestion. 2-NDBG (dilutions need to be standardized) will be added in for measuring the glucose uptake after insulin stimulation (with 10ng/ul insulin and without). Briefly, PCV of mature adipocyte is washed three times after digestion. Krebs Ringer Bicarbonate Hepes Buffer (Ph 7.4) is used to dilute the cells into 5% -10% to use for the assay. 10ng/ul of insulin or vehicle control are added to the fixed volume of cell suspension and incubated for 30 mins. Cell reaction (2NDBG incorporation) will be counted at excitation/emission=485/535nm to detect the fluorescence in the mature cells.

12) Measurement of secretome from preadipocytes in culture

During the 2-weeks of adipogenic differentiation, we will collect the media of the preadipocytes on day 3, 7, and 14 of differentiation. Media will be harvested and spun, then frozen at -80C for future cytokine assays. The attached preadipocyte cell number in each well at the time of seeding will be used for cytokine normalization (expressed per number of cells) as described¹⁷.

13) Measurement of secretome from adipose tissue

Briefly, 30 mg of adipose tissue is incubated in buffer (Krebs-Ringer Solution) plus albumin (3ml/g of tissue) for approximately 5–30min to reduce contamination of the tissue with blood cells and soluble factors. At the conclusion of this brief incubation, the tissue explants are flash centrifuged for 30s at 400g in order to remove blood cells. The explants (~100mg/ml ratio) are then incubated at 37C for 48 hrs in suspension culture under aseptic conditions. After 48 hrs incubation, tissues are spun down, and the

supernatant is collected and flash frozen for future cytokine assays. We use the Human Adipocyte (cell culture samples, Cat# HADCYMAG-61K) panel to assay 11 cytokines by luminex (Millipore). Cytokines are expressed per mg tissue.

14) Adipose cell size distribution

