Surgical biopsy tissues (EAT, PAT, or SAT) are washed in PBS to remove excess blood, and then cut into small pieces (30-50 mg weighted for each test). Cut tissue biopsy is treated with ERTUGLIFLOZIN (-/+, 25 μ M) for overnight in CO2 incubator (37C), with culture medium (CM) collected for cytokine release (-/+ Ertu). Tissue biopsy is washed with wash buffer (1x) and then treated with lipolysis condition (Basal, Isoproterenol (15nM), and Isoproterenol (15nM) + Insulin (3nM)), for 1 hr in in CO2 incubator (37C). Then culture medium (CM*) collected for free glycerol release assay (lipolysis) by a commercial kit (EGLY-200).

Treatment

- List the clinical dosage/dosage form, route, and dose regimen:

Tissue will be collected during surgery for cell culture (in vitro, direct effects) work.

Collateral Research

- Include biomarkers, PK, etc.

The planned study already has multiple endpoints. Optional pilot studies: miRNA from current EAT study, co-culture treated and untreated adipocytes with human cardiomyocytes and ipscendothelial cells (stem cell lab [name], Stanford).

Statistical Plans

- Include justification for clinical sample size and primary hypothesis testing:

Primary end point: Isoproterenol-stimulated lipolysis:

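### Glucose uptake is measured only at zero and near-saturating insulin, so IMGU estimates maximal insulin response and would barely register a change in insulin sensitivity

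*Combined protocol and SAP*

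**What the plan says.** The Background and Rationale ends with the hypothesis: "We hypothesize that ertugliflozin will enhance lipolysis, improve insulin sensitivity, decrease adipose cell size, and reverse inflammatory phenotype in EAT". The Hypothesis section repeats the idea as "smaller adipocytes with increased insulin sensitivity".

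Study Design/Clinical Plan, item 2, assigns the glucose-uptake work to bariatric subcutaneous and visceral fat, comparing mock with drug-treated culture: "Mature cells from bariatric samples will be tested for lipolysis, insulin-mediated glucose uptake, gene expression". These cells are there to support the epicardial results.

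Laboratory Methods, item 11 (mature adipocytes), measures "glucose uptake after insulin stimulation (with 10ng/ul insulin and without". The procedure confirms two conditions only: "10ng/ul of insulin or vehicle control are added to the fixed volume of cell suspension and incubated for 30 mins". Item 7 (cells differentiated in culture) has one stimulated level: "10ug/ml of insulin is added to the cells to stimulate the glucose release". That is the same concentration, since 1 ug/ml equals 1 ng/ul. Neither item describes a lower insulin level, a dose-response curve or an EC50.

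The one nanomolar insulin condition is in Laboratory Methods, item 17, where explants with and without drug are exposed to "Isoproterenol (15nM) + Insulin (3nM" nM). The readout there is glycerol release, not glucose uptake.

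The closing sentence of Statistical Plans places IMGU among the other endpoints, analysed by paired and unpaired t-tests. No effect size or power is given for it.

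**The concern.** Insulin sensitivity is usually understood as the position of the dose-response curve: a more sensitive cell reaches a given response at less insulin. Maximal responsiveness is the height of the plateau. If the only stimulated level is on the plateau in both the drug and the vehicle arm, stimulated minus basal uptake shows the height and hides a shift in position.

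Two wrong conclusions then become possible. A real gain in sensitivity with an unchanged maximum would look like no effect. A change in maximal uptake could be taken for a change in sensitivity. Recruiting more subjects is no practical remedy, because almost none of the signal is present at that insulin level.

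**Working it through.** **Inputs from the documents.** Insulin at 0 and 10 ng/ul (Laboratory Methods, item 11); 10 ug/ml (item 7); 3 nM in the explant lipolysis assay (item 17).

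**Assumptions, not in the documents.** Insulin molar mass 5,808 g/mol (range tried 5,700 to 6,000). Insulin-stimulated uptake above basal follows a simple saturating curve, R = C/(C + EC50), as a fraction of its maximum. EC50 is between 0.1 and 100 nM. The drug halves the EC50 and leaves the maximum unchanged.

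**Step 1: convert the concentration.** 10 ng/ul = 10 ug/ml = 0.010 g/L. Then 0.010 / 5,808 = 1.722 × 10⁻⁶ mol/L, or 1,722 nM. The range over the assumed molar masses is 1,667 to 1,754 nM.

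**Step 2: compare with the explant level.** 1,722 / 3 = 574 (range 556 to 585). This only sets the scale, because 3 nM is used for a different response.

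**Step 3: effect of halving the EC50.** The relative rise in response is

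(C + EC50)/(C + EC50/2) − 1 = (EC50/2)/(C + EC50/2).

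Example at EC50 = 100 nM: 50/(1,722 + 50) = 2.8%. Example at EC50 = 10 nM: 5/(1,722 + 5) = 0.29%.

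| Assumed EC50 (nM) | Response at 1,722 nM, % of maximum | Rise at 1,722 nM | Rise at 3 nM |
|---|---|---|---|
| 0.1 | 99.99 | 0.003% | 1.6% |
| 0.3 | 99.98 | 0.009% | 4.8% |
| 1 | 99.94 | 0.03% | 14.3% |
| 3 | 99.83 | 0.09% | 33.3% |
| 10 | 99.42 | 0.29% | 62.5% |
| 30 | 98.29 | 0.86% | 83.3% |
| 100 | 94.51 | 2.8% | 94.3% |

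**Step 4: how high the EC50 would have to be.** For a halved EC50 to change the response at 1,722 nM by 10%, (EC50/2)/(1,722 + EC50/2) = 0.10, so EC50/2 = 1,722/9 and EC50 is about 383 nM.

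**Reading.** At the planned level the assay is nearly blind to a doubling of sensitivity across the whole range. The last column shows that a lower level can reveal the shift, but also that 3 nM need not be low enough: with an EC50 of 0.1 to 0.3 nM it too is near the plateau.

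**The case against.** Several points on the other side stand.

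- **The trial has other evidence on insulin action.** A reader might infer that the trial cannot test its insulin-sensitivity hypothesis at all. The documents do not support that. The explants in item 17 include epicardial tissue and compare drug with no drug at 3 nM insulin, which bears on insulin's suppression of lipolysis. Only the glucose-uptake evidence is limited.
- **IMGU is a supporting endpoint.** Lipolysis is primary and cytokine expression secondary. The Background hypothesis concerns epicardial fat, whereas the mature-cell assay uses bariatric samples.
- **The plan does not say that IMGU will be reported as sensitivity.** It gives no definition of the term, and Study Design/Clinical Plan, item 1, names glucose uptake and insulin sensitivity as two things. A reader might infer that a true improvement is bound to be reported as no effect. That would follow only for a pure shift in EC50 with an unchanged maximum, and the documents specify no such pattern. Maximal stimulated uptake is a legitimate endpoint under its own name.
- **3 nM is not a like-for-like level.** A reader might take it as the effective level for glucose uptake, and so as the level to add. Nothing in the documents shows that it is effective or submaximal for 2-NDBG uptake.

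One objection is weaker. If 10 ng/ul were a stock, the final level would be lower. But the text reads as the assay condition and states no dilution, and a dilution of about 574-fold would be needed to reach 3 nM.

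None of this alters the main fact: no glucose-uptake assay in the plan has a submaximal insulin level over the EC50 range considered.

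**Conclusion.** The point holds within limits. For an EC50 up to about 100 nM, the comparison of zero with about 1.7 uM insulin estimates maximal insulin response. A halved EC50 would move it by at most about 3%, and by less than 0.3% if the EC50 is 10 nM or lower. This rests on a simple saturating curve, an assumed molar mass, an EC50 range that the documents do not supply, and 10 ng/ul being the final concentration.

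The consequence is that neither a null nor a positive IMGU result at this level is evidence on insulin sensitivity as a shift of the curve. It can still show a change in basal or maximal uptake. It is a worthwhile correction to a supporting endpoint and leaves the primary endpoint and the explant evidence untouched.

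**What to change.** **For samples not yet processed:**

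1. Run a short insulin titration as part of assay set-up. Item 11 already says that the 2-NDBG dilutions remain to be standardised, so this is a natural place for it.
2. Add one level shown by the titration to be submaximal for 2-NDBG uptake, in both the drug and the vehicle arm. Do not assume that 3 nM qualifies.
3. Prespecify the sensitivity contrast as uptake at the submaximal level minus basal uptake. Report it also as a fraction of uptake at 10 ng/ul minus basal uptake, and compare the arms on both.

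**For all samples, including those already processed:** label the 10 ng/ul result maximal insulin response, and state that it will not be taken as evidence for or against a change in insulin sensitivity. Apply the same label to the cultured-cell assay in item 7.

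**Cost.** A titration, a few extra wells per bariatric sample and a few sentences in the plan. Item 2 of Study Design/Clinical Plan says that bariatric samples give more fat than epicardial ones, so material is less likely to be the constraint. Timing may be: the Study Information section reports 61 enrolled against a goal of 36, 43 of them bariatric, and the assay needs fresh cells. The sensitivity contrast will exist only for samples still to come; if there are none, the relabelling alone remains.

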Two 30 mg samples of osmium-fixed tissue are incubated in a water bath at 37°C for 48 h and then washed as previously described¹⁸, after which adipose cell size was determined via a Beckman Coulter (Miami, FL, USA) Multisizer III with a 400- μ m aperture. The effective cell-size range using this aperture is 20 to 240 μ m, excluding preadipocytes and cells of mononuclear origin. The instrument is set to count 6,000 particles and the fixed-cell suspension is diluted so that coincident counting is less than 10%. After collection of pulse sizes, the data is expressed as particle diameters and displayed as histograms of counts against diameter using linear bins and a linear scale for the x-axis. Cell size distribution is described via a mathematical model (non-linear least squares function nls, R 1.9(<http://r-project.org>))), as previously described¹⁸, in which a single formula using 7 cell-size parameters describes the cell distribution, in which the small cells are represented by a double exponential, and the large cells by a Gaussian curve, as follows: $y = h1 \exp(-(x - x0)/w1) + h2 \exp(-(x - x0)/w2 + hp \exp(-(x - cp)^2/wp))$ where x = cell diameter, and x0 = the smallest diameter; h1 and w1 = height and width of the first exponential; h2 and w2 = height and width of the second exponential; and hp, cp, and wp = height, center, and width-squared of the Gaussian curve. From these fitted curves the following estimates are possible: 1) Peak diameter – middle of the Gaussian: reflects mean size of mature adipose cells; 2) AUC Gaussian: represents fat storage capacity; 3) Width of the Gaussian - this represents the variability in size of mature cells. This is evident from mouse models utilizing curve fitting from multisizer curves in which weight gain is associated first with increase in peak diameter, followed by widening of the Gaussian and an increase in the number/fraction of small cells, consistent with studies from other groups in humans, and rodents, showing “hypertrophy” followed by “hyperplasia”. When the curve widens and flattens, it is associated with increased number of cells and likely represents movement of small cells into the large cell subfraction rather than shrinking size due to lipolysis; 4) % small cells –represents the proportion of all adipose cells that reside in the small cell subfraction, defined as diameter less than the nadir. An increased number of cells in this fraction indicates either increased adipogenesis, with movement from preadipocytes to small adipocyte population now apparent on multisizer, or an inability of small cells to move into the large cell population with resultant accumulation.

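### The Gaussian area in the cell-size analysis is a large-cell count, not a measure of fat storage capacity, and the printed fitting formula has a bracket that needs correcting or confirming

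*Combined protocol and SAP*

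**What the plan says.** All of the relevant text is in Laboratory Methods, item 14.

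- **Data.** "The instrument is set to count 6,000 particles", and the results are shown as "histograms of counts against diameter using linear bins and a linear scale for the x-axis". The bin width is not given.
- **Model in words.** One equation with seven size parameters is fitted to each histogram. Its components are given as follows: "the small cells are represented by a double exponential, and the large cells by a Gaussian curve".
- **Model in symbols.** After the first exponential the formula continues "h2 \exp(-(x - x0)/w2 + hp \exp(-(x - cp)^2/wp", followed by two closing brackets. The text then defines hp, cp and wp as the height, centre and squared width of the Gaussian.
- **Estimates.** Peak diameter is the middle of the Gaussian. The second estimate is "AUC Gaussian: represents fat storage capacity". The others are the width of the Gaussian and the percentage of small cells, meaning those below the nadir.

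No scaling of the area to tissue mass, cell number or cell volume is stated. The Hypothesis section expects SGLT2i treatment to yield "smaller adipocytes with increased insulin sensitivity". Statistical Plans names isoproterenol-stimulated lipolysis as the primary endpoint and inflammatory cytokine expression as the secondary one. It does not mention cell size.

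**The concern.** There are two separate questions.

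First, an area under a curve of counts, taken from a sample whose total count is fixed in advance, can only say how those counts are divided. The amount of fat a depot holds or could hold depends on how many cells there are and how large they are. If the area is read as storage capacity, a change in the mix of counted cells could be reported as a change in storage, and a real loss of lipid from large cells could be reported as no change.

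Second, the formula and the sentence describing it are different models. In the printed form the Gaussian multiplies the second exponential on the log scale instead of being added to it, so hp is not a height and hp, cp and wp do not carry the meanings given to them. Anyone coding from the page would obtain parameters that cannot be read as the text reads them.

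**Working it through.** **Inputs from item 14:** 6,000 particles; counts on linear diameter bins; 7 parameters; size range 20 to 240 µm (x0 taken as 20).

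**Assumed, because the documents do not give them:** 1 µm bins; 40–60% small cells; Gaussian centre 90–120 µm and SD 12–20 µm; exponential widths 5 and 20 µm.

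**The plan's own figure.** h1, w1, h2, w2, hp, cp and wp make 7 parameters, with x0 fixed as the smallest diameter. The stated 7 is reproduced.

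**Part 1: what the area measures (additive model, as the prose describes).**

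Area of hp·exp(−(x−cp)²/wp) = hp·√(π·wp), in counts × µm. Divided by bin width, this is the number of counted cells in the large-cell component. With a 50% share it is 6,000 × 0.5 = 3,000 at 1 µm bins; the same cells give 1,500 at 0.5 µm bins and 6,000 at 2 µm bins. Tissue with twice as many cells and the same share gives the same area.

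Mean large-cell volume = (π/6)(cp³ + 3·cp·SD²), with SD² = wp/2. With SD 15 µm (SD² = 225) and 3,000 large cells:

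| Centre (µm) | cp³ + 3·cp·225 | Volume relative to 100 µm | Area |
|---|---|---|---|
| 90 | 789,750 | 0.74 | 3,000 |
| 100 | 1,067,500 | 1.00 | 3,000 |
| 110 | 1,405,250 | 1.32 | 3,000 |
| 120 | 1,809,000 | 1.69 | 3,000 |

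A peak falling from 100 to 90 µm lowers large-cell volume by 1 − 0.74 = 26% with no change in the area. The two can also move in opposite directions: at 110 µm with 45.45% large cells, the area is 2,727 (−9%) while volume is 0.909 × 1.316 = 1.20 times its starting value (+20%).

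**Part 2: the printed formula.**

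Counting brackets gives depth 0 at the h2 term, depth 1 at the hp term and depth 0 at the end. The brackets balance and the Gaussian is nested:

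y = h1·exp(−(x−x0)/w1) + h2·exp(−(x−x0)/w2 + hp·exp(−(x−cp)²/wp))

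Put additive-model values into it (h2 = 60, w2 = 20, hp = 79.8, cp = 100). At x = cp the second term is 60·exp(−80/20 + 79.8), about 10^34.7 counts, so hp cannot be a height in this form.

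Noise-free additive histograms of 6,000 cells were then refitted with the nested form, over seven combinations of the assumed inputs:

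| Quantity | True (additive) | Nested fit |
|---|---|---|
| Centre cp | 90–120 µm | 4.1 to 9.0 µm too high (105.4 for 100 at 50% large, SD 15) |
| Height hp | 60–100 | 3.4–4.5 |
| wp | 288–800 | about 2.5 to 3.7 times too large |
| hp·√(π·wp) | 2,400–3,600 | about 200–324 |
| Mode of the whole fitted curve | 90–120 µm | 0.6 to 1.1 µm too high |

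R² was 0.998–0.999 throughout, so a good fit would not reveal the wrong form.

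**How the parts relate.** They are alternatives. The area is a cell count only under the additive form, and there cp is exactly the peak diameter. Closing the bracket after w2 therefore repairs peak diameter but leaves Part 1 untouched.

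**The case against.** - **The bracket is probably typographical.** The prose, the parameter labels and the reference to a previously described method all point to the additive form. The same sentence has a surplus closing bracket after the R web address, and the text was read from PDF. This stands: a reader might infer that peak diameter is wrong, but nothing in the documents shows that the nested form was coded.
- **Capacity is not current lipid content.** The plan offers storage capacity as an interpretation, so disagreement with volume is not in itself an error. This stands in part. The area still contains no total cell number and no cell size, so it supports no reading of capacity either.
- **Shrinkage is not missed.** Peak diameter is the direct measure, and it moves from 100 to 90 µm in the example. This stands.
- **The area is not a duplicate of the percentage of small cells.** A reader might infer that they are one number reported twice. They are not: one is a fitted component, the other a cut at the nadir. Take h1 = 200, w1 = 8, h2 = 60, w2 = 25, hp = 50, cp = 100, wp = 450. The Gaussian share is 1,880/(1,600 + 1,500 + 1,880) = 37.8% and the share below the nadir is 57.5%, which do not sum to 100%. Moving w2 from 15 to 40 takes the Gaussian share from 42.9% to 32.0%, while the small-cell share barely moves (55.9% to 55.4%).
- **Little rests on it.** The drug-versus-vehicle outcomes in Study Design and the explant protocol in item 17 do not include cell sizing, and no comparison of the Gaussian area is stated. This stands and limits the importance.

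**Conclusion.** The point holds in two limited parts and is minor.

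The Gaussian area, as described, is up to bin width the number or share of large cells among 6,000 counted. A conclusion about fat storage capacity drawn from it would be unsound. That follows from the fixed count and the absence of any stated scaling; the 26% figure is illustrative and rests on the assumed SD of 15 µm and 50% large cells.

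The printed formula contradicts its own description and should be corrected or confirmed. The 4 to 9 µm shift in cp applies only if the nested form was coded, and its size depends on the assumed curve parameters.

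Cell size appears in the hypothesis but is neither the primary nor the secondary endpoint, so no principal result depends on either part.

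**What to change.** 1. Print the model as y = h1·exp(−(x−x0)/w1) + h2·exp(−(x−x0)/w2) + hp·exp(−(x−cp)²/wp), and confirm that the nls code uses it.
2. Report the Gaussian area as the large-cell count or fraction, with the bin width, or state how it is scaled to tissue mass or cell number. Draw no storage conclusion from the unscaled area.
3. If a lipid-storage measure is wanted, add mean large-cell volume from the same fit, (π/6)(cp³ + 3·cp·wp/2), or the sum of π·d³/6 over recorded pulses above the nadir. Describe it as the volume of the counted cells, not as total capacity.

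The cost is a text correction, a check of the code and a few lines of R on data already recorded, with no new assay. The drawback is that the volume measure would not be directly comparable with area values reported previously.
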